(e.g., radiation therapy or radiofrequency ablation), unless disease progression has subsequently been radiologically confirmed after focal/local therapy. It may be the case that, on occasion, the largest lesion does not lend itself to reproducible measurement in which circumstance the next largest lesion which can be measured reproducibly should be selected. Lymph nodes merit special mention since they are normal anatomical structures which may be visible by imaging even if not involved by tumor. Pathological nodes which are defined as measurable and may be identified as target lesions must meet the criterion of a short axis of ≥ 15 mm by CT scan. Only the short axis of these nodes will contribute to the baseline sum. The short axis of the node is the diameter normally used by radiologists to judge if a node is involved by solid tumor. Nodal size is normally reported as two dimensions in the plane in which the image is obtained (for CT scan this is almost always the axial plane; for MRI the plane of acquisition may be axial, sagittal or coronal). The smaller of these measures is the short axis. For example, an abdominal node which is reported as being 20 mm x 30 mm has a short axis of 20 mm and qualifies as a malignant, measurable node. In this example, 20 mm should be recorded as the node measurement. All other pathological nodes (those with short axis ≥ 10 mm but < 15 mm) should be considered non-target lesions. Nodes that have a short axis < 10 mm are considered non-pathological and should not be recorded or followed. A sum of the diameters (longest for non-nodal lesions, short axis for nodal lesions) for all target lesions will be calculated and reported as the baseline sum diameters. If lymph nodes are to be included in the sum, then as noted above, only the short axis is added into the sum. The baseline sum diameters will be used as reference to further characterize any objective tumor regression in the measurable dimension of the disease.

Non-Target Lesions

All other lesions (or sites of disease) including pathological lymph nodes should be identified as non-target lesions and should also be recorded at baseline. Measurements are not required and these lesions should be followed as ‘present’, ‘absent’, or in rare cases ‘unequivocal progression’ (more details to follow). In addition, it is possible to record multiple nontarget lesions involving the same organ as a single item on the case record form (e.g., ‘multiple enlarged pelvic lymph nodes’ or ‘multiple liver metastases’).

Guidelines for Evaluation of Measurable Disease

All measurements should be recorded in metric notation, using calipers if clinically assessed. All baseline evaluations must be performed within 28 days prior to randomization, and preferably no more than 28 days before the initiation of treatment.

Method of assessment

The same method of assessment and the same technique should be used to characterize each identified and reported lesion at baseline and during follow-up. Imaging based evaluation should

always be done rather than clinical examination unless the lesion(s) being followed cannot be imaged but are assessable by clinical exam.

Clinical lesions: Clinical lesions will only be considered measurable when they are superficial and ≥ 10 mm diameter as assessed using calipers (e.g., skin nodules). For the case of skin lesions, documentation by color photography including a ruler to estimate the size of the lesion is suggested. As noted above, when lesions can be evaluated by both clinical exam and imaging, imaging evaluation should be undertaken since it is more objective and may also be reviewed at the end of the study.

Chest X-ray: Chest CT is preferred over chest X-ray, particularly when progression is an important endpoint, since CT is more sensitive than X-ray, particularly in identifying new lesions. However, lesions on chest X-ray may be considered measurable if they are clearly defined and surrounded by aerated lung.

CT, MRI: CT is the best currently available and reproducible method to measure lesions selected for response assessment. This guideline has defined measurability of lesions on CT scan based on the assumption that CT slice thickness is 5 mm or less. When CT scans have slice thickness greater than 5 mm, the minimum size for a measurable lesion should be twice the slice thickness. MRI is also acceptable in certain situations (e.g., for body scans).

Ultrasound: Ultrasound is not useful in assessment of lesion size and should not be used as a method of measurement. Ultrasound examinations cannot be reproduced in their entirety for independent review at a later date and, because they are operator dependent, it cannot be guaranteed that the same technique and measurements will be taken from one assessment to the next. If new lesions are identified by ultrasound in the course of the study, confirmation by CT or MRI is advised. If there is concern about radiation exposure at CT, MRI may be used instead of CT in selected instances.

Endoscopy, laparoscopy: The utilization of these techniques for objective tumor evaluation is not advised. However, they can be useful to confirm complete pathological response when biopsies are obtained or to determine relapse in studies where recurrence following CR or surgical resection is an endpoint.

Tumor markers: Tumor markers alone cannot be used to assess objective tumor response. If markers are initially above the upper normal limit, however, they must normalize for a patient to be considered in CR. Because tumor markers are disease specific, instructions for their measurement should be incorporated into protocols on a disease specific basis. Specific guidelines for both CA-125 response (in recurrent ovarian cancer) and PSA response (in recurrent prostate cancer), have been published. In addition, the Gynecologic Cancer Intergroup

has developed CA125 progression criteria which are to be integrated with objective tumor assessment for use in first-line studies in ovarian cancer.

Cytology, histology: These techniques can be used to differentiate between PR and CR in rare cases if required by protocol (for example, residual lesions in tumor types such as germ cell tumors, where known residual benign tumors can remain). When effusions are known to be a potential adverse effect of treatment (e.g., with certain taxane compounds or angiogenesis inhibitors), the cytological confirmation of the neoplastic origin of any effusion that appears or worsens during treatment can be considered if the measurable tumor has met criteria for response or SD in order to differentiate between response (or SD) and PD.

Evaluation of target lesions

This section provides the definitions of the criteria used to determine objective tumor response for target lesions.

Complete Response (CR): Disappearance of all target lesions. Any pathological lymph nodes (whether target or non-target) must have reduction in short axis to <10 mm.

Partial Response (PR): At least a 30% decrease in the sum of diameters of target lesions, taking as reference the baseline sum diameters.

Progressive Disease (PD): At least a 20% increase in the sum of diameters of target lesions, taking as reference the smallest sum on study (this includes the baseline sum if that is the smallest on study). In addition to the relative increase of 20%, the sum must also demonstrate an absolute increase of at least 5 mm. (Note: the appearance of one or more new lesions is also considered progression).

Stable Disease (SD): Neither sufficient shrinkage to qualify for PR nor sufficient increase to qualify for PD, taking as reference the smallest sum diameters while on study.

Evaluation of non-target lesions

This section provides the definitions of the criteria used to determine the tumor response for the group of non-target lesions.

While some non-target lesions may actually be measurable, they need not be measured and instead should be assessed only qualitatively at the time points specified in the protocol.

Complete Response (CR): Disappearance of all non-target lesions and normalization of tumor marker level. All lymph nodes must be non-pathological in size (<10 mm short axis).

Non-CR/Non-PD: Persistence of one or more non-target lesion(s) and/or maintenance of tumor marker level above the normal limits.

Progressive Disease (PD): Unequivocal progression of existing non-target lesions. (Note: the appearance of one or more new lesions is also considered progression).

Target Lesions	Non-target Lesions	New Lesions	Overall Response
CR	CR	No	CR
CR	Non-CR/non-PD	No	PR
CR	Not evaluated	No	PR
PR	Non-PD or not all evaluated	No	PR
SD	Non-PD or not all evaluated	No	SD
Not all evaluated	Non-PD	No	NE
PD	Any	Yes or No	PD
Any	PD	Yes or No	PD
Any	Any	Yes	PD

Abbreviations: CR: complete response; NE: not evaluated; PD: progressive disease; PR: partial response; SD: stable disease.

Note: Patients with a global deterioration of health status requiring discontinuation of investigational product without objective evidence of disease progression at that time should be classified as having “symptomatic deterioration.” Every effort should be made to document the objective progression, even after discontinuation of investigational product. In some circumstances, it may be difficult to distinguish residual disease from normal tissue. When the evaluation of CR depends on this determination, it is recommended that the residual lesion be investigated (fine needle aspirate/biopsy) before confirming the CR status.

Confirmatory Measurement/Duration of Response

Confirmation

In non-randomized studies where response is the primary endpoint, confirmation of PR and CR is required to ensure responses identified are not the result of measurement error. This will also permit appropriate interpretation of results in the context of historical data where response has traditionally required confirmation in such studies. However, in all other circumstances, i.e., in randomized studies (phase II or III) or studies where SD or progression are the primary endpoints, confirmation of response is not required since it will not add value to the interpretation of study results. However, elimination of the requirement for response confirmation may increase the importance of central review to protect against bias, in particular

in studies which are not blinded. In the case of SD, measurements must have met the SD criteria at least once after study entry at a minimum interval (in general not less than 6–8 weeks) that is defined in the study protocol.

Duration of overall response

The duration of overall response is measured from the time measurement criteria are first met for CR/PR (whichever is first recorded) until the first date that recurrent or PD is objectively documented (taking as reference for PD the smallest measurements recorded on study). The duration of overall CR is measured from the time measurement criteria are first met for CR until the first date that recurrent disease is objectively documented.

Duration of stable disease

Stable disease is measured from the start of the treatment (in randomized studies, from date of randomization) until the criteria for progression are met, taking as reference the smallest sum on study (if the baseline sum is the smallest, this is the reference for calculation of PD). The clinical relevance of the duration of SD varies in different studies and diseases. If the proportion of patients achieving SD for a minimum period of time is an endpoint of importance in a particular study, the protocol should specify the minimal time interval required between two measurements for determination of SD. Note: The DOR and SD as well as the PFS are influenced by the frequency of follow-up after baseline evaluation. It is not in the scope of this guideline to define a standard follow-up frequency. The frequency should take into account many parameters including disease types and stages, treatment periodicity and standard practice. However, these limitations of the precision of the measured endpoint should be taken into account if comparisons between studies are to be made.

Appendix 8

Health Outcomes Assessment: EORTC QLQ-C30

ENGLISH

EORTC QLQ-C30 (version 3)

We are interested in some things about you and your health. Please answer all of the questions yourself by circling the number that best applies to you. There are no "right" or "wrong" answers. The information that you provide will remain strictly confidential.

Please fill in your initials:
 Your birthdate (Day, Month, Year):
 Today's date (Day, Month, Year): 31

	Not at All	A Little	Quite a Bit	Very Much
1. Do you have any trouble doing strenuous activities, like carrying a heavy shopping bag or a suitcase?	1	2	3	4
2. Do you have any trouble taking a long walk?	1	2	3	4
3. Do you have any trouble taking a short walk outside of the house?	1	2	3	4
4. Do you need to stay in bed or a chair during the day?	1	2	3	4
5. Do you need help with eating, dressing, washing yourself or using the toilet?	1	2	3	4

During the past week:

	Not at All	A Little	Quite a Bit	Very Much
6. Were you limited in doing either your work or other daily activities?	1	2	3	4
7. Were you limited in pursuing your hobbies or other leisure time activities?	1	2	3	4
8. Were you short of breath?	1	2	3	4
9. Have you had pain?	1	2	3	4
10. Did you need to rest?	1	2	3	4
11. Have you had trouble sleeping?	1	2	3	4
12. Have you felt weak?	1	2	3	4
13. Have you lacked appetite?	1	2	3	4
14. Have you felt nauseated?	1	2	3	4
15. Have you vomited?	1	2	3	4
16. Have you been constipated?	1	2	3	4

Please go on to the next page

ENGLISH

During the past week:

	Not at All	A Little	Quite a Bit	Very Much
17. Have you had diarrhea?	1	2	3	4
18. Were you tired?	1	2	3	4
19. Did pain interfere with your daily activities?	1	2	3	4
20. Have you had difficulty in concentrating on things, like reading a newspaper or watching television?	1	2	3	4
21. Did you feel tense?	1	2	3	4
22. Did you worry?	1	2	3	4
23. Did you feel irritable?	1	2	3	4
24. Did you feel depressed?	1	2	3	4
25. Have you had difficulty remembering things?	1	2	3	4
26. Has your physical condition or medical treatment interfered with your family life?	1	2	3	4
27. Has your physical condition or medical treatment interfered with your social activities?	1	2	3	4
28. Has your physical condition or medical treatment caused you financial difficulties?	1	2	3	4

For the following questions please circle the number between 1 and 7 that best applies to you

29. How would you rate your overall health during the past week?

1 2 3 4 5 6 7

Very poor

Excellent

30. How would you rate your overall quality of life during the past week?

1 2 3 4 5 6 7

Very poor

Excellent

© Copyright 1995 EORTC Quality of Life Group. All rights reserved. Version 3.0

Appendix 9
Health Outcomes Assessment: EORTC QLQ-BR23

ENGLISH

EORTC QLQ - BR23

Patients sometimes report that they have the following symptoms or problems. Please indicate the extent to which you have experienced these symptoms or problems during the past week.

During the past week:	Not at All	A Little	Quite a Bit	Very Much
31. Did you have a dry mouth?	1	2	3	4
32. Did food and drink taste different than usual?	1	2	3	4
33. Were your eyes painful, irritated or watery?	1	2	3	4
34. Have you lost any hair?	1	2	3	4
35. Answer this question only if you had any hair loss: Were you upset by the loss of your hair?	1	2	3	4
36. Did you feel ill or unwell?	1	2	3	4
37. Did you have hot flushes?	1	2	3	4
38. Did you have headaches?	1	2	3	4
39. Have you felt physically less attractive as a result of your disease or treatment?	1	2	3	4
40. Have you been feeling less feminine as a result of your disease or treatment?	1	2	3	4
41. Did you find it difficult to look at yourself naked?	1	2	3	4
42. Have you been dissatisfied with your body?	1	2	3	4
43. Were you worried about your health in the future?	1	2	3	4

During the past four weeks:	Not at All	A Little	Quite a Bit	Very Much
44. To what extent were you interested in sex?	1	2	3	4
45. To what extent were you sexually active? (with or without intercourse)	1	2	3	4
46. Answer this question only if you have been sexually active: To what extent was sex enjoyable for you?	1	2	3	4

Please go on to the next page

ENGLISH

During the past week:	Not at All	A Little	Quite a Bit	Very Much
47. Did you have any pain in your arm or shoulder?	1	2	3	4
48. Did you have a swollen arm or hand?	1	2	3	4
49. Was it difficult to raise your arm or to move it sideways?	1	2	3	4
50. Have you had any pain in the area of your affected breast?	1	2	3	4
51. Was the area of your affected breast swollen?	1	2	3	4
52. Was the area of your affected breast oversensitive?	1	2	3	4
53. Have you had skin problems on or in the area of your affected breast (e.g., itchy, dry, flaky)?	1	2	3	4

Appendix 10
Health Outcomes Assessment: EQ-5D-5L

(English version for the UK)

SAMPLE

UK (English) v. 2 © 2009 EuroQol Group. EQ-5D™ is a trade mark of the EuroQol Group

Under each heading, please tick the ONE box that best describes your health TODAY

MOBILITY

- I have no problems in walking about
- I have slight problems in walking about
- I have moderate problems in walking about
- I have severe problems in walking about
- I am unable to walk about

SELF-CARE

- I have no problems washing or dressing myself
- I have slight problems washing or dressing myself
- I have moderate problems washing or dressing myself
- I have severe problems washing or dressing myself
- I am unable to wash or dress myself

USUAL ACTIVITIES (e.g. work, study, housework, family or leisure activities)

- I have no problems doing my usual activities
- I have slight problems doing my usual activities
- I have moderate problems doing my usual activities
- I have severe problems doing my usual activities
- I am unable to do my usual activities

PAIN / DISCOMFORT

- I have no pain or discomfort
- I have slight pain or discomfort
- I have moderate pain or discomfort
- I have severe pain or discomfort
- I have extreme pain or discomfort

[figure not shown]
ANXIETY / DEPRESSION

- I am not anxious or depressed
- I am slightly anxious or depressed
- I am moderately anxious or depressed
- I am severely anxious or depressed
- I am extremely anxious or depressed

- We would like to know how good or bad your health is TODAY.
- This scale is numbered from 0 to 100.
- 100 means the best health you can imagine.
0 means the worst health you can imagine.

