2. TOXICITIES REQUIRING INVESTIGATIONAL PRODUCT DOSE ADJUSTMENTS

NERATINIB PLUS CAPECITABINE

General Toxicities

Guidelines for dose adjustments of **neratinib** and **capecitabine** for general toxicities due to combination of neratinib plus capecitabine are shown in Table A2. 1.

Table A2. 1 General Toxicities Requiring Dose Adjustment of Neratinib and Capecitabine

NCI CTCAE v.4.0	Action
Grade 2 adverse reaction	
• 1st appearance	• Hold neratinib and capecitabine until event resolves to Grade \leq 1; then resume both drugs at the starting dose level.
• 2nd appearance	• Hold neratinib and capecitabine until event resolves to Grade \leq 1; then resume neratinib at 160 mg and capecitabine at 1100 mg/m ² (550 mg/m ² BID).
• 3rd appearance	• Hold neratinib and capecitabine until event resolves to Grade \leq 1; then resume neratinib at 120 mg and capecitabine at 750 mg/m ² (375 mg/m ² BID).
• 4th appearance	• Discontinue neratinib and capecitabine permanently.
Grade 3 adverse reaction	
• 1st appearance	• Hold neratinib and capecitabine until event resolves to Grade \leq 1; then resume neratinib at 160 mg and capecitabine at 1100 mg/m ² (550 mg/m ² BID).
• 2nd appearance	• Hold neratinib and capecitabine until event resolves to Grade \leq 1; then resume neratinib at 120 mg and capecitabine at 750 mg/m ² (375 mg/m ² BID).
• 3rd appearance	• Discontinue neratinib and capecitabine permanently.
Grade 4 adverse reaction	
• 1st appearance	• Discontinue neratinib and capecitabine permanently OR if Investigator deems it to be in the patient's best interest to continue, hold neratinib and capecitabine until resolved to Grade \leq 1; then resume neratinib at 120 mg and capecitabine at 750 mg/m ² (375 mg/m ² BID).

Abbreviations: BID, twice daily; NCI CTCAE v.4.0: National Cancer Institute Common Terminology Criteria for Adverse Events Version 4.0.

Gastrointestinal Toxicity

Guidelines for adjusting doses of **neratinib** and **capecitabine** in the event of gastrointestinal toxicities are shown in Table A2. 2.

Table A2. 2 Gastrointestinal Toxicities Requiring Dose Adjustment of Neratinib and Capecitabine

NCI CTCAE v.4.0	Actions

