
Grade 1 Diarrhea: Increase of <4 stools per day over baseline; mild increase in output compared to baseline. OR Grade 2 Diarrhea: Increase of 4-6 stools per day over baseline; moderate increase in ostomy output compared to baseline. Lasting ≤5 days OR Grade 3 Diarrhea: Increase of ≥7 stools per day over baseline; incontinence; hospitalization indicated; severe increase in ostomy output compared to baseline; limiting self-care and activities of daily living. Lasting ≤2 days
	
 • Adjust antidiarrheal treatment per the guidelines for management of diarrhea at the first onset of diarrhea (refer to Section 7.1.1). • Continue neratinib and capecitabine at full doses. • Instruct patient to follow dietetic recommendations in the guidelines for management of diarrhea (refer to Section 7.1.1). • Fluid intake of ~2 L/day should be maintained to avoid dehydration. • Once the event resolved to Grade ≤1 or baseline, start loperamide 4 mg with each subsequent neratinib administration.

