
Persisting and intolerable Grade 2 Diarrhea: lasting >5 days despite treatment with optimal medical therapy, or associated with fever, dehydration, or Grade 3-4 neutropenia. OR Grade 3 Diarrhea: lasting >2 days despite treatment with optimal medical therapy, or associated with fever, dehydration, or Grade 3-4 neutropenia. OR Any Grade 4 diarrhea: Life-threatening consequences: urgent intervention indicated.
	
 • Adjust antidiarrheal treatment per the guidelines for management of diarrhea at the first onset of diarrhea (refer to Section 7.1.1). • Hold neratinib and capecitabine until recovery to Grade ≤1 or baseline. • Instruct patient to follow dietetic recommendations of the guidelines for management of diarrhea. • Fluid intake of ~2 L/day should be maintained by IV, if needed. • If recovery occurs: 
 ○ ≤1 week after withholding treatment, resume same doses of neratinib and capecitabine. ○ Within 1-3 weeks after withholding treatment, reduce neratinib dose to 160 mg and maintain the same dose of capecitabine. • If event occurs a second time and the neratinib dose has not already been decreased, reduce neratinib dose to 160 mg (maintain the same dose of capecitabine). If neratinib dose has already been reduced, then reduce the dose of capecitabine to 1100 mg/m² (550 mg/m² BID)^a (maintain the same dose of neratinib). • If subsequent events occur, reduce the dose of neratinib or capecitabine to the next lower dose level in an alternate fashion (i.e., reduce capecitabine to 750 mg/m² (375 mg/m² BID)^b if neratinib was previously reduced, or reduce neratinib to 120 mg if capecitabine was previously reduced).

NCI CTCAE v.4.0	Actions
	
 Once the event resolved to Grade ≤ 1 or baseline, start loperamide 4 mg with each subsequent neratinib administration.

Abbreviations: BID: twice daily; IV: intravenous; L: liter; NCI CTCAE v.4.0: National Cancer Institute Common Terminology Criteria for Adverse Events Version 4.0.

^aSince capecitabine is provided as 150 mg or 500 mg tablets, it is recommended that the capecitabine dose reduction(s) is rounded down to the nearest 500 mg or multiple of 150 mg for the BID dose. If the patient's body surface area is >2.0 , the standard of care for the study center can be utilized for capecitabine mg/m^2 dosing.

Pulmonary Toxicity

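### Table A2.2 gives two opposite dosing instructions for Grade 3 diarrhea of 2 days or less with fever, dehydration or Grade 3-4 neutropenia, and nothing says which governs

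*Protocol*

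**What the plan says.** Table A2.2 (Protocol Appendix 2, neratinib plus capecitabine) sorts diarrhea into two rows.

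- **First row.** Entry is by grade and duration only: any Grade 1, Grade 2 for up to 5 days, or Grade 3 for up to 2 days. The dosing action is "Continue neratinib and capecitabine at full doses". The fluid advice is "Fluid intake of ~2 L/day should be maintained to avoid dehydration".
- **Second row.** Entry for Grade 3 is a duration above 2 days despite optimal therapy, "or associated with fever, dehydration, or Grade 3-4 neutropenia". The Grade 2 entry has the same complication limb but opens with the label "Persisting and intolerable Grade 2 Diarrhea". Any Grade 4 event is included. The dosing action is "Hold neratinib and capecitabine until recovery to Grade" 1 or lower, or baseline. The fluid advice is "Fluid intake of ~2 L/day should be maintained by IV, if needed". For repeat events the row adds: "If event occurs a second time and the neratinib dose has not already been decreased, reduce neratinib dose to 160 mg".

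Three other places bear on the point. Section 6.1.3 treats the dose rules as a floor and lets investigators do more. Section 7.1.1 separates uncomplicated from complicated diarrhea, using the same three features, but only for diet, antidiarrheals, fluids and antibiotics. Table A2.6 keeps neratinib at its current dose during Grade 3 or 4 hematologic toxicity and adjusts only capecitabine.

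**The concern.** A patient with Grade 3 diarrhea on its first or second day who is also febrile, dehydrated or severely neutropenic satisfies both rows. One row says to carry on at full dose and the other says to stop both drugs. A site cannot do both.

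Section 7.1.1 names diarrhea as the main toxicity limiting neratinib dosing, and this table is the rule that sites follow for it. The overlap also falls when decisions are made. Any complicated Grade 3 event seen within its first 2 days meets both rows at that moment, even if it later lasts longer. Early contact is planned: Section 7.1.1 requires calls 1, 2 and 3 days after the first neratinib dose, and Section 2.2.3.4 reports a median diarrhea onset of 2 days in the Phase 1/2 combination study.

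There is also a later consequence. If the first event is handled under the first row, a site may not count it when deciding whether the next one is a second occurrence, which is what triggers the reduction to 160 mg.

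**Working it through.** No arithmetic applies. The check is to run Grade 3 diarrhea through both rows and then look for a sentence that settles any conflict. Optimal medical therapy is assumed to be in use.

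| Grade 3 event | First row (continue) | Second row (hold) |
|---|---|---|
| Up to 2 days, no complication | Yes | No |
| Over 2 days, no complication | No | Yes |
| Over 2 days, with complication | No | Yes |
| Up to 2 days, with complication | **Yes** | **Yes** |

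Only the last line conflicts. The candidate tie-breakers are:

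1. **Structure of the second row.** Grade 3 beyond 2 days is already held by the duration limb. The complication limb adds almost nothing unless it governs short events. This points to a hold.
2. **Fluid advice.** The first row's advice aims to prevent dehydration, while the second row's provides for IV fluids. This suggests that the first row was written for patients who are not yet dehydrated. It also points to a hold.
3. **Section 6.1.3.** If the rules are a minimum, an investigator may hold. That permits the safer action but does not rank the rows.
4. **Section 7.1.1.** The split by complications shows intent, but that block gives no study-drug rule. Its closing sentence says only that patients who do not respond to treatment may need an interruption or reduction.
5. **Table A2.1.** Its instruction, "Hold neratinib and capecitabine until event resolves to Grade" 1 or lower, could apply separately if the complication is itself a Grade 2 or higher adverse reaction. That depends on the case and does not rank the rows of Table A2.2.

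No section of the protocol or SAP states precedence. One could read the 2-day threshold as applying to both limbs of the second row, which would remove the overlap. The comma and the word 'or' do not favor that reading, and it would leave early complicated Grade 3 diarrhea under continued full dosing.

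Table A2.6 raises a secondary question. Where the complication is Grade 3-4 neutropenia, it continues neratinib while the second row of Table A2.2 holds it.

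With the first row's Grade 3 criterion restricted to uncomplicated events, the last line of the table becomes No / Yes and the other three lines do not change.

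**The case against.** The strongest reply is that the text already resolves itself. A specific criterion normally prevails over a general one, and only a hold gives the second row's complication limb any real work. Table A2.9 in Arm B is laid out similarly: its Grade 1 and Grade 2 rows do not exclude complications, and a later row for complicated Grade 1 or 2 events holds both drugs. Readers would naturally let that later row take over. Sites also have a signed Investigator Checklist and Patient Instructions, which may clarify the matter, although their content is not in these documents.

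Much of this stands. It makes a hold the likely choice and limits the weight of the point. It does not supply the missing sentence, and the first row's plain instruction still applies to a febrile or dehydrated Grade 3 patient. For Grade 3 itself, Table A2.9 has no such overlap, since it holds both drugs for any Grade 3 diarrhea.

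Two further replies also stand in part. Table A2.6 concerns capecitabine adjustment, so its neratinib line can be read as saying only that the blood count alone requires no neratinib change. That makes it a secondary point, to be settled in the same sentence. For Grade 2, whether a short complicated event overlaps depends on whether "Persisting and intolerable Grade 2 Diarrhea" limits the complication limb. A reader might infer that Grade 2 has the same defect outright, but the wording does not support that. Imposing an override there could change Arm A dosing under some readings, rather than clarify it.

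**Conclusion.** The overlap is real for short, complicated Grade 3 diarrhea in Arm A, and it should be corrected. It is a patient-safety correction to a dosing rule and has no effect on alpha, power or event counts.

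The conclusion rests on the plain wording of the two rows and on the absence of any precedence sentence in the protocol or SAP. It does not assume that sites would choose wrongly.

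Two stronger inferences are not supported. A reader might conclude that the protocol directs full-dose continuation in these patients. It does not: the second row applies too, and the context favors it. A reader might also try to size the problem from the 23% Grade 3/4 diarrhea rate in the Phase 1/2 study (Section 2.2.3.4). That figure is not split by duration or by complication, so it gives no rate for the affected events.

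**What to change.** In Table A2.2:

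- Change the first row's Grade 3 criterion to: *Lasting ≤2 days, without fever, dehydration, or Grade 3-4 neutropenia.*
- Add one sentence: *The second row governs Grade 3 diarrhea with any of these features regardless of duration, including the neratinib hold where Table A2.6 would otherwise continue neratinib.*
- For Grade 2, ask the sponsor to state whether the second row's opening label limits the complication limb. Do not impose an answer.

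This can go in the next amendment or a site clarification letter and needs no new data or procedures. The downside is a few more short treatment holds in Arm A at sites that would have followed the first row. Under the existing second-row rule, recovery within a week of withholding returns both drugs to the same doses; a repeat event brings the stated reductions.
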